8.2. Subject Exclusion Criteria for ADULT Subjects

Exclusion Criteria Specific for ADULT Subjects:

At Visit 1 (Screening) and Visit 2 (Baseline, Day 1), subjects with any of the following ocular conditions in either eye or with any of the following non-ocular conditions or characteristics are not eligible to participate in the study:

General

1. Females who are pregnant, nursing or planning a pregnancy.
2. Subjects with known or suspected drug or alcohol abuse.
3. Current or planned participation in any other clinical trial involving an investigational product or device within 4 weeks prior to Visit 1 (Screening) or at any time during this trial.
4. Subjects who have been exposed to DE-117 prior to Visit 1 (Screening).

Medications / Therapies

5. Intended or current use of the following prohibited medications/therapies during the study duration:

All ocular medications other than sodium chloride/potassium chloride ophthalmic solution, cataract treatment agents (e.g., glutathione, pirenoxine), Vitamin B ₁₂ formulation (e.g., cyanocobalamin), over-the-counter dry eye artificial tears/drops, and study medications.
All systemic medications for ocular hypotensive (e.g., oral or intravenous CAI, oral glycerol).
Any ocular, periocular, inhaled, nasal or systemic corticosteroids including joint injection, etc.
Lacrimal/punctal occlusion via plug (s) or cautery.

6. Subjects who cannot safely discontinue use of ocular hypotensive medications during the wait/washout period.
7. Subjects who will be required to initiate or modify any systemic or topical medication known to affect IOP (e.g., β -adrenergic antagonists, α -adrenergic agonists, calcium channel blockers, angiotensin-converting enzyme [ACE] inhibitors, and angiotensin II receptor blockers [ARB]). Subjects using the above medications must be on a stable dose use for at least 30 days prior to Visit 1 (Screening) and during the study duration.
8. Use of contact lenses within 2-3 weeks prior to Visit 2 (Baseline, Day 1) until end of treatment in either eye (2 weeks for soft contact lens wearers, and 3 weeks for rigid contact lens wearers).
9. Any ocular surgery or ocular laser treatment within 180 days prior to Visit 1 (Screening) and throughout the study in either eye.

10. History of ocular surgery specifically intended to lower IOP (e.g., laser trabeculoplasty, filtering surgery, tube shunt, Minimally Invasive Glaucoma Surgery (MIGS), or trabeculotomy) in either eye.
11. History of keratorefractive surgery (e.g., RK, PRK, LASIK) in either eye.
12. Allergy, hypersensitivity or contraindications to EP2 receptor agonists, beta-blockers, benzalkonium chloride (BAK) or any other components of the study medications, or other study related procedures/medications. This also includes subjects with a history or presence of contraindications to beta-blocker therapy, such as chronic obstructive pulmonary disease (e.g., chronic bronchitis, emphysema), bronchial asthma, second or third degree atrioventricular block, uncontrolled congestive heart failure.

Diseases

13. Presence of advanced glaucoma (e.g., visual field mean deviation worse than -12 dB) in either eye.
14. Presence of any corneal abnormality or other conditions interfering with or preventing reliable Goldmann applanation tonometry (e.g. Fuch's dystrophy or significant corneal surface abnormality) in either eye.
15. Presence of any active severe external ocular disease, inflammation, or infection of the eye and/or eyelids in either eye.
16. Presence or history of macular edema or known risk factors for macular edema in either eye.
17. History of severe ocular trauma in either eye.
18. History of iritis and/or uveitis in either eye.
19. History of retinal detachment, proliferative diabetic retinopathy, or any retinal disease that may be progressive during the time course of the study in either eye.
20. Presence or history of any disease or condition that in the opinion of the study Investigator may put the subject at significant risk, may confound study results, or may interfere significantly with the subject's participation in the study (e.g., recurrent corneal erosion syndrome, uncontrolled cardiovascular disease etc.).
21. Any decision by the Investigator or Medical Monitor to terminate a subject in screening or declare any subject ineligible for any sound medical reason.

8.3. Subject Inclusion Criteria for PEDIATRIC Subjects

Inclusion Criteria Specific for PEDIATRIC Subjects:

At Visit 1 (Screening), the pediatric subjects must meet all of the following inclusion criteria:

1. Parent/legal guardian signed written informed consent on the Institutional Review Board (IRB)/Ethics Committee (EC) approved Informed Consent Form (ICF) and patient assent has been given as applicable.
2. The patient and parent/legal guardian should agree to comply with study restrictions, treatment plan, procedures and keep scheduled visits.

3. Be \geq 1 year and less than 18 years old on the date of signing the ICF.
4. If a subject is a female of childbearing potential she must have a negative urine pregnancy test and must use at least one of the following acceptable contraceptive methods during the study (as well as for 4 weeks following last dose in study).
 - Abstinence
 - Hormonal contraceptive method (including oral or transdermal contraceptives, injectable progesterone, progestin subdermal implants, progesterone-releasing intrauterine devices [IUDs]) initiated at least 28 days prior
 - Placement of a copper-containing IUD
 - Condom with spermicidal foam/gel/film/cream/suppository
 - Vasectomized male partner (surgery at least 6 months prior)

Male subjects capable of fathering children should use/ practice an acceptable contraceptive method, such as abstinence, condom or vasectomy (surgery at least 6 months prior) or other contraceptive method deemed adequate by the investigator throughout the course of the study (as well as for 12 weeks following last dose in study).

5. Must have a diagnosis of pediatric glaucoma or OHT in one or both eyes, including primary (congenital and juvenile open angle glaucoma) and secondary glaucoma. For a child with pediatric glaucoma due to secondary causes, the Investigator or study site should discuss the case with the Medical Monitor prior to subject enrollment.
6. Must have elevated IOP to such a level that investigator deems pharmacologic intervention with IOP-lowering medication to be clinically necessary in at least one eye.
7. Must have a sufficiently clear cornea that allows for a complete ophthalmic examination.
8. Anterior chamber angle grade \geq 2 (Shaffer scale) in each eye, based on gonioscopy performed at Visit 1 (Screening), or historical gonioscopy performed within 12 months prior.

In addition to continuing to meet inclusion criteria 6 (elevated IOP) and 7 (clear cornea), the subject must meet the following criterion at Visit 2 (Baseline, Day 1):

9. Completed the required wait/washout period.

8.4. Subject Exclusion Criteria for PEDIATRIC Subjects

Exclusion Criteria Specific for PEDIATRIC Subjects:

At Visit 1 (Screening) and Visit 2 (Baseline, Day 1), subjects with any of the following ocular conditions in either eye or with any of the following non-ocular conditions or characteristics are not eligible to participate in the study. Exception: criteria 8, 9 and 10 only apply to the eye being considered for study treatment. E.g., if only the non-treated eye has a history of LASIK, the other eye may still qualify for participation and treatment in the study if the subject meets all other criteria.

General

1. Females who are pregnant, nursing or planning a pregnancy.
2. Subjects with known or suspected drug or alcohol abuse.
3. Current or planned participation in any other clinical trial involving an investigational product or device within 4 weeks prior to Visit 1 (Screening) or at any time during this trial.
4. Subjects who have been exposed to DE-117 prior to Visit 1 (Screening).

Medications / Therapies

5. Intended or current use of the following prohibited medications/therapies during the study duration:

All ocular medications other than sodium chloride/potassium chloride ophthalmic solution, cataract treatment agents (e.g., glutathione, pirenoxine), Vitamin B₁₂ formulation (e.g., cyanocobalamine), over-the-counter dry eye artificial tears/drops, and study medications.

All systemic medications for ocular hypotensive (e.g., oral or intravenous CAI, oral glycerol).

Any ocular, periocular, inhaled, nasal or systemic corticosteroids including joint injection, etc.

Lacrimal/punctal occlusion via plug (s) or cautery.

6. Subjects who cannot safely discontinue use of ocular hypotensive medications during the wait/washout period.
7. Subjects who will be required to initiate or modify any systemic or topical medication known to affect IOP (e.g., β -adrenergic antagonists, α -adrenergic agonists, calcium channel blockers, angiotensin-converting enzyme [ACE] inhibitors, and angiotensin II receptor blockers [ARB]). Subjects using the above medications must be on a stable dose use for at least 30 days prior to Visit 1 (Screening) and during the study duration.
8. Use of contact lenses within 2-3 weeks prior to Visit 2 (Baseline, Day 1) until end of treatment (2 weeks for soft contact lens wearers, and 3 weeks for rigid contact lens wearers).
9. Any ocular surgery (including goniotomy or glaucoma surgery) or ocular laser treatment within 180 days prior to Visit 1 (Screening) and throughout the study.
10. History of keratorefractive surgery (e.g., RK, PRK, LASIK).
11. Allergy, hypersensitivity or contraindications to EP2 receptor agonists, beta-blockers, benzalkonium chloride (BAK) or any other components of the study medications, or other study related procedures/medications. This also includes subjects with a history or presence of contraindications to beta-blocker therapy, such as chronic obstructive

pulmonary disease (e.g., chronic bronchitis, emphysema), bronchial asthma, second or third degree atrioventricular block, uncontrolled congestive heart failure.

Diseases

12. Presence of advanced glaucoma in either eye.
13. Presence of any corneal abnormality or other conditions interfering with or preventing reliable tonometric measurements (e.g., Fuch's dystrophy or significant corneal surface abnormality) in either eye.
14. Presence of any active severe external ocular disease, inflammation, or infection of the eye and/or eyelids in either eye.
15. Presence or history of macular edema or known risk factors for macular edema in either eye.
16. Aphakia or pseudophakia
17. Single sighted subject
18. History of severe ocular trauma in either eye.
19. History of iritis and/or uveitis in either eye.
20. History of retinal detachment, proliferative diabetic retinopathy, or any retinal disease that may be progressive during the time course of the study in either eye.
21. Presence or history of any disease or condition that, in the opinion of the study Investigator, may put the subject at significant risk (such as contraindication to the use of Timolol Maleate Ophthalmic Solution 0.5%), may confound study results, or may interfere significantly with the subject's participation in the study (e.g., recurrent corneal erosion syndrome, uncontrolled cardiovascular disease etc.).
22. Any decision by the Investigator or Medical Monitor to terminate a subject in screening or declare any subject ineligible for any sound medical reason.

8.5. Subject Withdrawal Criteria

An early termination occurs when a subject who provides written informed consent ceases participation in the study, regardless of circumstances, before the completion of the study. Subjects may be voluntarily discontinued from study medication or withdrawn from the study at any time for any reason. In addition, the Principal Investigator or Medical Monitor may discontinue the study drug administration or terminate a subject's study participation due to any of the following reasons:

- AE (e.g., not compatible with study continuation)
- Non-compliance with study drug
- Lack of efficacy (e.g., IOP exceeds 34 mmHg in either eye after randomization)
- Progressive disease

- Protocol deviation (e.g., not fulfilling eligibility criteria)
- Pregnancy
- Voluntary withdrawal by subject at any time for any reason
- Lost to follow-up (e.g., no contact is possible)
- Death
- Other

If the study drug administration is discontinued prior to Visit 5, they should be encouraged to still participate in follow-up study visits until Visit 5 on an observational basis.

[figure not shown]
If the study drug administration is discontinued prior to Visit 5, then to the extent possible, all procedures for Early Termination will be performed on the day of early drug discontinuation as per [Table 3](#) (for adult subjects) or [Table 4](#) (for pediatric subjects). Subjects who are discontinued from the study early will not be replaced.

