9.2. Concomitant Medications or Therapies

Medication or therapy considered necessary for the subject's welfare may be given at the discretion of the Investigator. Subjects may continue participation in the study if the instituted medication or therapy will not interfere with the evaluation of the study medication. Whenever possible, medications should be administered in dosages that remain constant throughout the study. Any treatment other than the study medication during the study duration will be considered as a concomitant treatment. The information of concomitant treatment must be recorded in the subject's source documents and on the eCRF.

- Concomitant medication: name of medication, route of administration, treated eye(s) (if applicable), dose, frequency, indication, start date and stop date.
- Concomitant therapy: name of therapy, treated eye(s) (if applicable), indication, start date and stop date.

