9.3. Treatment Compliance

To obtain reliable efficacy and safety data, the following precautions will be taken to ensure compliance with the treatment regimen during the study:

- Subjects will receive verbal and written instructions for proper instillation of the study medication, the dosing regimen, and the conditions of the study medication storage.
- Subjects will be reminded at study visits to consistently dose at the same time of the day.
 - Twice daily at 08:00 and 20:00 [± 60 min] through Visit 2 to 5

- Once daily at 20:00 [± 60 min] through Visit 5 to 8 for adult subjects only
- Subjects will be reminded of the evening instillation of the study drug on the day before Visit 3 through Visit 8/Early Termination respectively.
- Subjects will be reminded that the morning instillation of the study drug at each visit through Visit 3 to 5 will be done at the clinic.
- For adult subjects, since subjects must have a diagnosis of OAG or OHT in both eyes, both eyes should be treated for the duration of the study, even if only one eye is eligible per IOP inclusion criteria.
For pediatric subjects, if only one eye has a diagnose of glaucoma or OHT, the fellow eye doesn't have to be treated by the study medications for the duration of the study.
- Subjects will be queried regarding compliance with the protocol's dosing regimen at Visit 3 through Visit 8/Early Termination.
- Subjects will be counseled on proper dosing procedures and dosing schedule if the subject's compliance is not 100%.
- A subject's dosing compliance for a specific period is determined by the total number of days that subject followed the proper dosing procedures and dosing schedule. Stoppage of study medication use, overdosing of study medication, incorrect time of study medication administration, will be noted as non-compliance. The subject's dosing compliance will be recorded in the subject's source documents at Visit 3 through Visit 8/Early Termination.
- Subjects may be discontinued from the study at the discretion of the Investigator if the subject cannot be brought into compliance.

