**Table 8: Overview of Primary and Sensitivity Analysis Methods**

| Primary or Sensitivity Analysis | Statistical Method        | Analysis Population | Handling of Missing Data |
|---------------------------------|---------------------------|---------------------|--------------------------|
| Primary Analysis                | MMRM                      | FAS                 | Observed cases           |
| Sensitivity Analyses            | MMRM                      | PPS                 | Observed cases           |
|                                 | PMM with delta-adjustment | FAS                 | MI                       |

Abbreviations: FAS = full analysis set; MI = multiple imputation; MMRM = mixed-effects model for repeated measures; PMM = pattern-mixture model; PPS = per protocol set.

To assess the sensitivity to departure from MAR assumption, a PMM with delta-adjustment will be applied, as follows:

- a. Use Markov chain Monte Carlo (MCMC) to create monotone missingness first. Then obtain standard multiple imputations under MAR assumptions for missing IOP values using monotone regression. The missing data are filled in and 50 complete datasets are created. The seed that will be used in the SAS program is 13546.
- b. For each IOP value that had been missing because of (1) censoring after having received IOP-lowering rescue therapy; or because of (2) early study discontinuation due to lack of efficacy or AE, regardless of treatment arm, adjust these values by adding delta to the imputed values, where delta = 1.0 mmHg. The seed that will be used in the SAS program is 13546.
- c. Each of the 50 complete datasets will then be analyzed separately using the same MMRM as used for the primary analysis.
- d. The estimates obtained from the MMRM analysis of each complete dataset are combined for inference purposes.
- e. Repeat step b, c, d, with delta = 2.0, 3.0, 4.0, and 5.0 mmHg. The larger the value of delta that is required to reverse the conclusion of the primary analysis, the more robust the conclusion is considered to be.

The main part of the SAS code for the specified MMRM analysis and PMM are provided in [Appendix A](#) and [Appendix B](#), respectively.

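### Protocol 8.5 and 9.3 allow study participation, not only study drug, to be ended for non-compliance or protocol deviation, and the resulting missing IOP is stressed by no planned sensitivity analysis beyond missing at random

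*Protocol*

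**What the plan says.** Protocol 8.5 provides that the Principal Investigator or Medical Monitor "may discontinue the study drug administration or terminate a subject's study participation due to any of the following reasons". The list includes "Non-compliance with study drug" and "Protocol deviation (e.g., not fulfilling eligibility criteria"), and it names progressive disease separately from lack of efficacy. Protocol 9.3 adds: "Subjects may be discontinued from the study at the discretion of the Investigator if the subject cannot be brought into compliance".

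For subjects whose study drug is stopped before Visit 5, Protocol 8.5 says "they should be encouraged to still participate in follow-up study visits until Visit 5 on an observational basis". SAP 3.4 repeats this. The sentence is tied to stopping drug and does not limit the power to end participation. Protocol 8.5 also states: "Subjects who are discontinued from the study early will not be replaced".

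On the analysis side:

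- Protocol 14.7 and SAP 6.2.1 and 8 censor IOP only after non-study IOP-lowering therapy. Off-drug IOP without such therapy stays in.
- The primary analysis is an MMRM on observed cases (SAP 6.2.1, Table 8).
- The pattern-mixture analysis imputes all missing IOP under missing at random. It then adds delta (1.0 to 5.0 mmHg) only to values missing after rescue therapy or after "early study discontinuation due to lack of efficacy or AE" (SAP 8.1.1.2, step b).
- The trimmed-mean analysis is conditional. Its trigger counts only study drug discontinuation for lack of efficacy or AE.
- SAP 10.3 removes LOCF.

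**The concern.** A subject who is non-compliant, or found ineligible after randomization, can still have IOP measured. If the site stops only the drug and the subject keeps attending, those readings enter the primary analysis. If the site ends participation, the later readings do not exist and the model predicts them. The choice is made after randomization, at discretion, with no stated criterion.

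The recorded reason then decides whether the gap is stressed. An exit coded as lack of efficacy or AE receives delta. One coded as non-compliance, protocol deviation or progressive disease does not, at any delta. If some of these codes conceal poor tolerability or poor IOP control, and more so in one arm, the analysis that SAP 10.3 calls sufficient to judge robustness would not show it.

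Data that are kept can still be excluded from the PPS under SAP 5.4. Data never collected cannot be restored to the FAS.

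**Working it through.** **1. The plan's own figure.** Inputs from Protocol 14.3.1 and 14.3.2: 200 per arm, SD 4.0, correlation 0.6, true difference 0, two-sided 5%; success requires all nine upper limits ≤ 1.5 mmHg and at least five ≤ 1.0 mmHg. The standard error of a difference is 4.0 × √(2/200) = 0.40 mmHg. Simulation (400,000 draws, equal correlation among timepoints, normal approximation) gives:

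| Rule | Power |
|---|---|
| One timepoint, 1.5 | 96.3% |
| Three timepoints, all 1.5 | 91.6% |
| Nine timepoints, all 1.5 | 83.9% |
| Full rule, SD 4.0 | 72.5% |
| Full rule, baseline-adjusted, 200/arm | 94.2% |
| Full rule, baseline-adjusted, 180/arm | 90.5% |

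The baseline-adjusted rows assume that 0.6 also holds with baseline: residual SD 4.0 × √(1 − 0.36) = 3.2, residual correlation (0.6 − 0.36)/(1 − 0.36) = 0.375. The stated 90% is reachable under more than one variant. The documents do not say which was used, so it is not called wrong here.

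**2. Penalty applied to these exits.** Step b names rescue, lack of efficacy and AE. For non-compliance, protocol deviation and progressive disease the added amount is 0 mmHg at each delta from 1 to 5.

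**3. Possible shift.** Shift = (excess fraction missing in the DE-117 arm) × (true minus predicted IOP). Both factors are assumptions.

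| Excess in DE-117 arm | Gap 1 mmHg | Gap 5 mmHg |
|---|---|---|
| 2% | 0.02 | 0.10 |
| 5% | 0.05 | 0.25 |
| 10% | 0.10 | 0.50 |

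**4. Effect on the success rule.** The relevant error is declaring non-inferiority when the true difference is at the tighter margin. With a true difference of 1.0 mmHg at all nine timepoints and a favourable shift of 0.25 mmHg (Monte Carlo, repeat runs agree within about 0.1 point):

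| Setting | No shift | Shift at all nine | Shift at six (Week 1 unaffected) |
|---|---|---|---|
| SD 4.0, correlation 0.6 | 0.7% | 4.5% | 2.3% |
| SD 3.2, correlation 0.375 | 0.2% | 3.6% | 1.3% |

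For scale, a single upper-limit test at its margin errs 2.5% of the time. At a true difference of 1.5 mmHg the shifted probability stays below 0.1%. The extreme corner (10% and 5 mmHg, at all nine timepoints) makes a true 1.0 look like 1.0 − 0.5 = 0.5 mmHg, where the rule succeeds 17.6% (SD 4.0) or 25.2% (SD 3.2) of the time.

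**5. Balanced, similar loss.** No shift, only lost precision. At a true difference of 0, 5% missing per arm (190 per arm) lowers full-rule power from 94.2% to 92.5% (baseline-adjusted) or from 72.5% to 69.4% (SD 4.0).

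**The case against.** The case for leaving the text alone has real weight.

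- The wording is permissive, drug-only discontinuation is already available, and no document suggests that these exits will be common.
- Investigators are masked and both arms follow the same morning and evening bottle schedule, so one-sided loss is not the default expectation. SAP 7.1 reports disposition by arm and primary reason, so an imbalance would be visible.
- The exits are not data-free. SAP 3.4 asks for the Visit 8 assessments, which include IOP, at the Exit Visit where possible. SAP 4.1.4 maps readings to analysis visits by study day, and the MMRM conditions on the subject's own readings.
- Compliance is first queried at Visit 3, so Week 1 is largely unaffected by non-compliance exits.
- Keeping non-adherent subjects can pull the arms together, which favours non-inferiority. The PPS analysis is the counterweight and should stay.

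All of this limits the size. None of it brings these exits under a delta or gives a reason to stop measuring.

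Several stronger readings are not supported. A reader might infer that the plan ignores these missing values; it handles them, but only under missing at random. A reader might infer a bias towards DE-117; the documents fix no direction. At a true difference of 0.5 mmHg, a 0.25 mmHg shift at all nine timepoints moves success from about 17% to 43% (SD 4.0) or from 25% to 68% (SD 3.2), which might be read as false claims. DE-117 is non-inferior at 0.5 mmHg under both margins, so those are correct declarations. A reader might also want exit confined to withdrawn consent, loss to follow-up or death. That would contradict the pregnancy rule in Protocol 12.1.3 and the AE reason in 8.5. Finally, Protocol 9.2 says "Subjects may continue participation in the study if the instituted medication or therapy will not interfere with the evaluation of the study medication", but a change there adds little where the therapy lowers IOP, because those readings are censored anyway and post-rescue values already receive delta.

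**Conclusion.** The point holds as a cheap improvement, not as a demonstrated bias. Read together, the two documents let site discretion turn obtainable IOP into missing IOP for non-compliance and protocol deviation. Missing values from these exits, and from exits coded progressive disease, are examined only under missing at random.

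The size is unknown because no exit rate is given. Under the assumption that all excess loss falls in the DE-117 arm, 2–10% with a 1–5 mmHg gap shifts the difference by 0.02–0.50 mmHg at the affected timepoints, mainly Week 6 and Month 3. The 0.25 mmHg case produces a modest rise in wrong declarations at a true difference of 1.0 mmHg, and stays under 2.5% when Week 1 is unaffected. These figures also rest on equal correlation among timepoints and a normal approximation.

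**What to change.** 1. In Protocol 8.5 and 9.3, state that non-compliance and protocol deviation do not by themselves end study participation, and that these subjects are asked to continue the scheduled IOP and safety visits through Visit 5. Handle adherence and eligibility failures through the PPS. Leave the rules for stopping drug, and the AE, pregnancy and other clinical exits, unchanged.
2. In SAP 8.1.1.2 step b, add a pattern-mixture run that applies delta to all IOP values missing after discontinuation, whatever the recorded reason, including a version with delta in the DE-117 arm only. This also covers exits coded progressive disease. It cannot reach a subject removed before any post-baseline IOP, who is outside the FAS; only the first change helps there.

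Cost: a few sentences of protocol text and one more sensitivity analysis. The visits are already scheduled: at most three per subject, or two when the exit follows the Week 1 compliance query. Some subjects will decline them.
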